### **10.3.2 Serious Adverse Events**

For screen failure subjects, any SAEs occurring during the screening period (after informed consent) will be recorded in the subject’s source documentation only and will not be collected on the eCRF.

For enrolled subjects (i.e., those who successfully complete screening), all SAEs occurring after the signing of the ICF will be reported to [REDACTED] within 24 hours of the Investigator, designee, or site staff’s knowledge of the event regardless of relationship to study drug or relationship to disease under study. For enrolled subjects, all SAEs will be recorded in the AE section of the subject’s eCRF and source documentation.

In the event that the site experiences a temporary disruption of the EDC system a back-up paper SAE Reporting Form will be available for site staff to complete.

- Site staff will complete the paper SAE report form and e-mail it within 24 hours to the following address: [REDACTED]
- Only in cases where the email system is unavailable, site staff will send the SAE by fax to: [REDACTED].

If notification is made via email or fax, site staff must enter the SAE information into the EDC system as soon as the system becomes available.

All SAEs, regardless of causality, will be reported from the time the ICF is signed until 30 days following the last study visit or 30 days after last study treatment administration, whichever is longer. No formal study visit is required but Investigators must report any SAEs that occur during this 30-day period using the SAE reporting form provided; these will be entered into the safety database only. If the Investigator has not seen the subject at a clinic visit at the end of the reporting period, the Investigator must make reasonable efforts to contact the subject to inquire about SAEs.

All recorded SAEs, regardless of relationship to study treatment or relationship to disease under study, will be followed up until resolution, stabilization, or the subject is lost to follow-up and cannot be contacted. In circumstances where the Investigator is unable to make contact with the subject, the Investigator must provide a written statement to Aurinia confirming that the subject is lost to follow-up.

Any SAE considered to have a causal relationship (i.e., “related”) to the study treatment and discovered by the Investigator at any time after the study will be reported. A rationale for the assessment of a causal relationship must be provided by the Investigator. Any safety information that is obtained after the Follow-up Visit (Visit 9) will be documented in the safety database only.

A death occurring during the study or which comes to the attention of the Investigator within 30 days after the last study visit (including the Follow-up Visit) or until 30 days after the last study treatment administration, whichever is longer, whether considered drug-related or not, must be reported to Aurinia. If the subject died, the SAE report should include the cause of death as the event term and whether or not the death was related to study treatment, as well as the autopsy findings, if available. Preliminary reports will be followed by detailed descriptions which will include copies of hospital case reports, autopsy reports/certificates and other documents when requested and applicable.

Additional follow-up information must be reported in the eCRF within 24 hours of awareness following Investigator (or site) awareness of the information. The Investigator should not delay reporting an SAE in order to obtain additional information. Additional information, when available, should be reported to [REDACTED] by the reporting procedures described above.

The Investigator is encouraged to discuss with the study Medical Monitor when the issue of seriousness is unclear or questionable.

An investigator who receives an investigator safety report describing an SAE or other specific safety information (e.g., summary or listing of SAE) from the sponsor will file it along with the IB and will notify the Institutional Review Board (IRB)/Ethics Committee (EC)/Independent Ethics Committee (IEC), if appropriate according to local requirements.

The sponsor or its representative will be responsible for determining and, in turn, reporting SAEs to regulatory authorities according to the applicable regulatory requirements.

### **10.3.3 Pregnancy**

Pregnancy occurring in a female subject or in the partner of a male subject should be reported to [REDACTED] within 24 hours of becoming aware of the event using the pregnancy eCRF. The Investigator should counsel the subject, and in the case of a male subject, the subject’s partner, discuss the risks of continuing with the pregnancy and the possible effects on the fetus. A female subject must immediately inform the Investigator if she becomes pregnant during the study. Monitoring of the pregnancy in a female subject should continue until conclusion of the pregnancy. In case of a pregnancy in the partner of a male subject, the Investigator should obtain informed consent of the pregnant partner prior to monitoring of the pregnancy.

Women who have a positive pregnancy test during the study will be withdrawn from the study treatment and the procedures for withdrawal will be completed. The Medical Monitor must be contacted immediately.

All pregnancies, subject or partner of a subject, that occur during the study or come to the attention of the Investigator within 30 days after the last study visit (including the Follow-up Visit) or until 30 days after last study treatment administration, whichever is longer, must be reported to [REDACTED] by the reporting procedures described above.

The outcome of all such pregnancies (including normal births) should be followed up and documented, even if the subject was withdrawn from the study. Every effort should be made to gather information regarding the pregnancy outcome until 90 days (or otherwise as appropriate) post-partum. It will be the responsibility of Aurinia, together with the appropriate support of the Investigator, to obtain this information.

Complications of pregnancy such as abortion (spontaneous or induced), premature birth, or congenital abnormality are considered SAEs and should be reported following the reporting procedures as outlined in [Section 10.3.2, Serious Adverse Events](#). In the event that the site experiences a temporary disruption of the EDC system, a back-up paper Pregnancy Reporting Form will be available for site staff to complete.

## **11. CLINICAL ENDPOINTS COMMITTEE**

Not applicable.

## **12. DATA AND SAFETY MONITORING BOARD PROCEDURES**

Not applicable.

## **13. STATISTICAL ANALYSIS**

### **13.1 Statistical Methods**

Complete details of the statistical and analytical methods will be provided in a formal Statistical Analysis Plan (SAP), which will be finalized prior to the database lock. A general description of the planned methods is provided below. Any deviation from the SAP will be noted and explained in the clinical study report.

### **13.2 Sample Size and Power Calculations**

The total sample size will be approximately 20 subjects, with up to 10 subjects in Cohort 1 and at least 10 subjects in Cohort 2.

As this is an exploratory study, sample size calculations are not required. Descriptive statistics will be used and the results will only be hypothesis-generating.

### **13.3 Populations**

#### **13.3.1 Intent-to-Treat Set**

The intent-to-treat (ITT) set will consist of all enrolled subjects (non-screening failures) and will be used for all efficacy analyses.

#### **13.3.2 Safety Set**

The safety set will consist of all subjects who have taken at least 1 dose of study treatment.

#### **13.3.3 Per-protocol Set**

The per-protocol set (PPS) will consist of all subjects eligible from the ITT set who do not have any major protocol violations. Major protocol violations will be defined in the SAP.

### **13.4 Datasets**

Assessments taken at each visit will be analyzed using 2 different datasets. The first will be the observed cases dataset whereby all values collected will contribute to the dataset. A second dataset will be used for summaries and analyses incorporating data carried forward from a subject's last known value. This dataset will be referred to as the last observation carried forward dataset and as such, all subjects with any post-baseline efficacy assessment will contribute to the Week 24 analyses.

### **13.5 Background and Demographic Characteristics**

Demographic and clinical disease characteristics will be summarized.

## 13.6 Study Treatment

Compliance to the study treatment will be determined by dividing the number of softgel capsules taken by the expected number of softgel capsules to be taken (based on prescribed dose) over the subject's participation in the study.

Results will be summarized by means of descriptive statistics (n, mean, SD, median, minimum, and maximum) and frequency tables.

## 13.7 Concomitant Therapy

All concomitant medications will be coded by the World Health Organization Anatomical Therapeutic Chemical (ATC) Drug Reference List classification. The version used will be provided in the clinical study report.

## 13.8 Efficacy Evaluations

Primary and secondary endpoints will be assessed overall and for each individual cohort.

### 13.8.1 Primary Endpoint

The primary endpoint is the proportion of subjects with remission of proteinuria at Week 24 based on the following parameters:

- Complete remission: UPCR of  $<0.3$  mg/mg
- OR
- Partial remission: UPCR  $\geq 0.3$  mg/mg and  $<3.0$  mg/mg with  $>50\%$  reduction in UPCR from baseline

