- 15 First dose of study medication should occur in the morning the day after dispensing.

Notes: Subjects who discontinue therapy will be requested to attend their regularly scheduled study visits to the end of the study.

AE = Adverse event; BID = Twice daily; BP = Blood pressure; Disc. = Discontinuation; ECG = Electrocardiogram; FMV = First morning void; Min = Minimum; QoL = Quality of life; QTcF = QT interval duration corrected for heart rate using method of Fridericia; SAE = Serious adverse event; Wk= Week.

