#### **7.1.2.2 Corticosteroids**

Subjects entering the study with corticosteroids should have their steroid dose gradually titrated down until they achieve a daily dose of <10 mg/day prednisone by Week 12. The timing of the titration is at the discretion of the investigator, with a reduction of 5 mg/day every 2 weeks recommended. If clinically indicated, steroid tapering may start during the stability assessment period. A dose level may be maintained for up to 4 weeks or increased per investigator judgement following discussion with the Medical Monitor. Refer to [Appendix 4](#) for a conversion table of various formulations of steroids.

Corticosteroid treatment must be documented in the eCRF and source documentation.

When clinically indicated, subjects are allowed to be completely titrated off oral corticosteroids.

Corticosteroids should not be re-started in a patient whose dose has been reduced to zero, or initiated during the study in treatment-naïve patients, without prior discussion with the Medical Monitor.

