## **7.4 Voclosporin Dose Modification**

### **7.4.1 Discontinuation of Study Therapy Due to Non-response**

During the treatment period, any case where the subject experiences a worsening of proteinuria, or no improvement in proteinuria from baseline, once the highest permitted dose of study drug has been achieved, should be discussed with the Medical Monitor. Subjects may be allowed to add treatment with corticosteroids (IV or oral) while continuing with study drug, or may be discontinued from study treatment and transitioned to standard of care treatment.

If the dose level of 39.5 mg BID is determined for Cohort 2, any subject still on treatment in Cohort 1 who has completed 8 weeks of treatment and shown no meaningful improvement in proteinuria may have their dose increased to 39.5 mg BID per Investigator judgement and following discussion with the Medical Monitor.

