### **13.9 Statistical and Analytical Methods**

All statistical analyses relating to the primary and secondary objectives will be undertaken at study closure and will incorporate all available data.

In order to aid dose decisions for Cohort 2, an analysis of the first 5 or 6 subjects in Cohort 1 will be undertaken once the 5th or 6th subject reaches Week 12.

Given the small sample size, all analyses will be descriptive in nature.

Binary remission endpoints will be summarized using counts and proportions while continuous data will be summarized using means, SDs, medians, minimums and maximums. Kaplan-Meier methodology will be used for the analysis of time-to endpoints. Confidence intervals for proportions may be calculated but it is recognized that such intervals, being based on 20 patients, will be very wide. As an example, the 95% Clopper-Pearson CI for a proportion of 30% based on 20 patients is (11.9%, 54.3%).

The analysis of the primary endpoint, complete or partial remission of proteinuria at Week 24, will be conducted on the ITT set and confirmed with the PPS (if applicable). Remission of proteinuria will be summarized and an exact 2-sided 95% CI for the remission rate will be calculated.

The analyses of the secondary endpoints will incorporate the use of 2-sided 95% CIs and are described below:

- Binary endpoints will be summarized using counts and proportions along with exact 2-sided 95% CIs.
- Endpoints measured as a time-to-event will be displayed using Kaplan-Meier methodology. Median time-to-event along with 2-sided 95% CIs will be displayed.
- Other endpoints will be summarized by visit. Absolute values and differences between baseline and each time point up to and including Week 24 will be summarized using means and 2-sided 95% CIs. Changes between last on treatment value and post treatment follow-up will also be summarized.

Given the nature of the study, additional exploratory analysis will be undertaken as appropriate. This may include the reporting of individual case studies.

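### On the protocol text, a Week 24 remission reached after rescue steroids or standard of care counts in the primary remission rate for voclosporin

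*Combined protocol and SAP*

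**What the plan says.** The primary objective (section 3.1) is the efficacy of voclosporin in bringing proteinuria into remission after 24 weeks. The study is open label, and section 6 marks randomization as not applicable.

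**Endpoint.** Section 13.8.1: "The primary endpoint is the proportion of subjects with remission of proteinuria at Week 24 based on the following parameters". Complete remission is UPCR below 0.3 mg/mg. Partial remission is UPCR from 0.3 to below 3.0 mg/mg with a fall of more than 50% from baseline. There is no condition on still taking voclosporin or on other FSGS therapy.

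**Data.** The ITT set takes in every enrolled subject and serves all efficacy analyses (13.3.1). Of the two datasets in section 13.4, "The first will be the observed cases dataset whereby all values collected will contribute to the dataset"; the second carries forward the last known value. Section 13.9 says the analyses "will be undertaken at study closure and will incorporate all available data".

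**Rescue.** For worsening or unimproved proteinuria at the highest permitted dose, section 7.4.1 says "Subjects may be allowed to add treatment with corticosteroids (IV or oral) while continuing with study drug", or they "may be discontinued from study treatment and transitioned to standard of care treatment". On steroids taken at entry, section 7.1.2.2 adds: "A dose level may be maintained for up to 4 weeks or increased per investigator judgement following discussion with the Medical Monitor". It also says "Corticosteroids should not be re-started in a patient whose dose has been reduced to zero", but this bar lifts after discussion with the Medical Monitor.

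**Follow-up after stopping.** The Schedule of Events notes: "Subjects who discontinue therapy will be requested to attend their regularly scheduled study visits to the end of the study". The synopsis expects the same unless consent is withdrawn; section 5.6 qualifies it as where possible.

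**Deferred.** Section 13.1 leaves full methods to a formal SAP, to be final before database lock. Section 13.3.3 leaves the definition of major violations to that SAP.

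**The concern.** A subject whom the investigator and Medical Monitor have judged not to be improving on voclosporin can receive another active treatment and still enter the numerator as a success. In a randomized trial, a comparator arm with the same rescue policy would give such a rate a reference. Here there is none, so the reader cannot tell how much of the rate belongs to voclosporin.

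Rescue could plausibly work in this population. Exclusion criterion 5 removes subjects who stopped steroids for lack of response. Those enrolled are untreated, improving on steroids by at least 20% in UPCR, or were taken off steroids for poor tolerability.

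The protocol recognises the same kind of confounding elsewhere. Appendix 6 bars ACE inhibitor and ARB changes because they disturb the primary endpoint, and bars other immunosuppressants because they disturb the efficacy endpoints. It has no counting rule for the steroid rescue that it allows.

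**Working it through.** **1. Follow one subject through the rules.** The subject does not improve at the target dose, starts steroids or standard of care under 7.4.1, and has a UPCR meeting 13.8.1 at Week 24.

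- In the primary analysis set? Yes: enrolled, so ITT (13.3.1).
- In the observed-cases dataset? Yes: every collected value contributes (13.4).
- Different in the carried-forward dataset? No: the Week 24 value is present, so nothing is carried.
- Remission? Yes: only UPCR is tested (13.8.1).

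If the subject leaves before Week 24, Visit 8 is done at withdrawal (4.1, 9.2.3). The carried-forward dataset then uses the last known value, which may precede or follow rescue. It is not restricted to values before rescue. By contrast, the follow-up change endpoints in 13.8.2 do refer to the last on-treatment visit; the primary endpoint does not.

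**2. Reproduce the protocol's own figure.** Section 13.9 gives 11.9% to 54.3% for 30% of 20. The Clopper-Pearson limits for x of n are the 2.5% quantile of Beta(x, n−x+1) and the 97.5% quantile of Beta(x+1, n−x). With x = 6 and n = 20 this gives 11.9% to 54.3%, which agrees.

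**3. Effect per case.** Each counted rescue remission adds 1/n: 1/20 = 5 points overall, 1/10 = 10 points in a cohort of 10.

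| Remissions | Rate | 95% CI |
|---|---|---|
| 6/20 | 30.0% | 11.9 to 54.3% |
| 7/20 (one rescue remission added) | 35.0% | 15.4 to 59.2% |
| 8/20 (two added) | 40.0% | 19.1 to 63.9% |
| 3/10 | 30.0% | 6.7 to 65.2% |
| 4/10 (one added) | 40.0% | 12.2 to 73.8% |

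In the other direction, if one of six reported remissions followed rescue, recoding it gives 5/20 = 25.0% (8.7 to 49.1%).

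**4. How often (assumed).** The documents give neither the number rescued, k, nor the chance p that a rescued subject has a qualifying UPCR at Week 24. For 20 subjects the expected shift is 100·k·p/20 points, and the chance of at least one such count is 1 − (1 − p)^k.

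| k | p | Expected shift | At least one |
|---|---|---|---|
| 2 | 0.10 | 100 × 2 × 0.10/20 = 1.0 point | 1 − 0.90² = 19.0% |
| 2 | 0.50 | 100 × 2 × 0.50/20 = 5.0 points | 1 − 0.50² = 75.0% |
| 4 | 0.10 | 100 × 4 × 0.10/20 = 2.0 points | 1 − 0.90⁴ = 34.4% |
| 4 | 0.50 | 100 × 4 × 0.50/20 = 10.0 points | 1 − 0.50⁴ = 93.8% |

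These values of k and p are illustrative and are not bounds.

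**The case against.** **The SAP may settle it.** No single sentence says how a rescued subject is scored, section 13.4 does not name the dataset for the primary result, and the SAP is not available. This stands as a limit: the point concerns the protocol text. A reader might go on to infer that the rule will be picked once rescue outcomes are known. The open-label design and the database-lock deadline make that possible, but nothing in the documents shows it.

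**Using all values is a legitimate strategy.** A treatment-policy rate fits the ITT principle. That stands, provided it is chosen and labelled as such. Without a comparator it does not answer the objective in 3.1, so it belongs beside the main result.

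**Other outputs help.** The per-protocol analysis might remove some cases, remission at Weeks 8 and 12 is reported, and 13.9 allows individual case studies. These help a careful reader. The per-protocol set is not a dependable remedy: major violations are undefined, and steroids added under 7.4.1 are permitted.

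**The error need not always be upward.** One might infer that default counting can only inflate the rate. That is so only against a target that scores rescue as failure. Against what voclosporin alone would have achieved, the direction is open. A subject on voclosporin plus steroids may be a late voclosporin responder, and a subject switched away who does not remit might have remitted on continued voclosporin.

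**Steroids are already in the background.** Subjects may enter on steroids and taper. No rule on rescue isolates voclosporin fully; it only separates planned background treatment from treatment given because voclosporin was not working.

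**Conclusion.** The point holds, and it is minor. Following the stated rules, a subject rescued under 7.4.1 with a qualifying UPCR at Week 24, or as the last known value carried forward, is a remission in the ITT primary analysis. The rate then describes voclosporin plus rescue. Each case is worth 5 points in 20 subjects or 10 in a cohort of 10. The 5-point shift lies well inside the interval that the protocol already calls very wide.

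No test, power figure or success threshold is affected: 13.2 calls the results hypothesis-generating. The Cohort 2 dose decision uses Week 12 data. The remission rate is nevertheless the study's main output.

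Two further inferences are not supported:

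- That every subject who stops voclosporin will have a Week 24 value. Attendance is requested, and sought where possible.
- That section 1.1.1 implies about half of rescued subjects would remit. It puts steroid non-response at up to 50%, which is a ceiling on failure among FSGS patients generally. It neither fixes nor caps remission after voclosporin failure.

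The conclusion assumes that the SAP adds no rule and that at least one subject is rescued and then qualifies.

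**What to change.** Add to section 13.8.1, and carry into the SAP, that a subject is scored as non-remission at Week 24 in both datasets if, before the UPCR used for Week 24, the subject:

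- (a) starts, restarts or increases systemic corticosteroids for inadequate proteinuria response after reaching the highest permitted voclosporin dose (7.4.1); or
- (b) starts another systemic immunosuppressant for FSGS, or, after stopping voclosporin, starts, restarts or increases systemic corticosteroids for FSGS.

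The following do not trigger the rule: entry steroids held, tapered or briefly re-increased during dose escalation under 7.1.2.2, and a Cohort 1 increase to 39.5 mg BID. Subjects who stop voclosporin and receive no other FSGS therapy are analysed as observed and listed. The as-observed (treatment-policy) rate is reported as a sensitivity analysis.

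The cost is a few sentences and one table. No new visits or data are needed: the eCRF already records concomitant treatment with dose, dates and reason (7.6), corticosteroid use (7.1.2.2) and the reason for stopping study drug (5.6). The reported rate may be lower, and a late voclosporin responder who was given steroids counts as a failure in the main analysis; the sensitivity analysis shows this. Clause (a) relies on an open-label investigator's stated reason for the steroid change, so the affected subjects should be listed with their UPCR values.
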